## **Hypoglycemia analysis**

The participant-reported hypoglycemia will be analyzed using data from e-diary by

- Level 1 (defined by glucose value  $\geq 54$  to  $< 70$  mg/dL [3.0 to 3.9 mmol/L])
- Level 2 (defined by glucose  $< 54$  mg/dL [3.0 mmol/L])
- Level 3 (severe hypoglycemia), and
- the composite of Level 2 and Level 3.

The analysis periods of 0-6, 0-12, 0-26, 12-26 weeks of treatment will be considered.

Documented hypoglycemia will be defined as

- All documented hypoglycemia - episodes for the 24-hour period
- Non-nocturnal hypoglycemia - episodes during 6 AM to midnight, and
- Nocturnal hypoglycemia - episodes during midnight to 6 AM.

The incidence and rate of hypoglycemia will be summarized by treatment and analysis period for different types of hypoglycemia.

For continuous safety variables (for example, laboratory measures, vital signs and weight), MMRM or ANCOVA models will be used. For categorical safety variables (for example, AEs, incidence of hypoglycemia, treatment-emergent abnormal laboratory measurements), either Fisher's exact test or logistic regression will be used for treatment comparison.

Further details for assessing all safety measures will be described in the SAP.

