**Table 1 SAP Version History Summary**

Change	Description	Rationale
Version 2, Jan 22, 2024	
 
Edited the estimand for the composite measure of achieving HbA1c <7% at Week 26 without nocturnal hypoglycemia (<54 mg/dL [3.0 mmol/L], or severe) in Section 1.1.
 
Edited the analysis method for Time in glucose range between 70 and 180 mg/dL in Section 4.4.2.
 
Added sensitivity analyses in Section 4.3.3.
 
	To address FDA's feedback
	
 
Added DID-EQ to secondary objectives in Section 1.1 and statistical analysis method in Section 4.4.2.
 
Modified statistical method for PRO outcomes from MMRM to ANCOVA based on 1 post-baseline measure.
 
	Per protocol amendment (b) to address regulatory feedback
	
 
For laboratory analysis, removed shift analysis, treatment emergent high/low and add elevated or low values meeting specified levels.
 
Risk difference and 95% CI will be used for safety categorical data analysis.
 
	Per Lilly PSAP update in Version3
	
 
Added analysis for CGM-based hypoglycemia in Section 4.6.3.1.2.
 
Updated the definition for CGM-based hypoglycemia and other updates in Appendix 6.6
 
	Per CGM international consensus statement 2023
	
 
Added graphical testing figure and description in Section 2.1.
 
Added more subgroups in Section 4.7.2.
 
	As planned.
	
 
Updated data cutoff for glargine arm in EAS2 in Section 3.
 
	According to PK profile
	
 
Simplified immunogenicity section by referring to the PSAP in Section 4.7.1.
 
	To simplify the SAP
	Minor changes and reorganizations in the entire document.	For clarity.
	
 
Added treatment regimen analysis method for fasting serum glucose, fasting glucose from SBMG, and CGM parameters for supportive secondary endpoints and tertiary endpoints in Section 4.4.2 and Section 4.5.1
 
Modified missing data handling approach for nocturnal hypoglycemia for the composite endpoint of HbA1c <7% at Week 26 without nocturnal hypoglycemia in Section 4.4.1.
 
Added sensitivity analyses for CGM that includes all data in derived variables in Appendix 6.
 
	According to FDA's feedback

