TEAEs	The baseline period includes the screening/lead-in period up to the first dose of study treatment (AE Start Relative to Exposure Assessment in CRF is used to determine).	Safety analysis period starts after the first dose and ends at the last visit in the study including safety follow-up period.
Safety laboratory tests, vital signs and body weight	
The baseline will be the last non-missing assessment prior to or on the day of first dose of study treatment
 
Planned measurements at scheduled visits will be included.
	
All scheduled visits after the day of first dose up to Visit 802 for MMRM or ANCOVA
 
Planned measurements at scheduled visits will be included.

Analysis	Baseline Observations	Post-Baseline Observations
laboratory values elevated or low, vital signs and body weight categorical measures	
Starts from the screening visit and ends prior to or on the day of first dose of study treatment.
 
All available measurement at scheduled and unscheduled visits will be included. The baseline for weight will be the last non-missing value during the baseline period
	
Starts after the day of first dose of study treatment and ends at the last visit in the study including both treatment period and follow-up period.
 
All available measurement at scheduled and unscheduled visits in the specified analysis period will be included.

Anti-LY3209590 antibody	The baseline will be the last non-missing assessment prior to or on the day of first dose of study treatment	All scheduled and unscheduled measurement after the day of first dose of study treatment .
Patient-reported outcomes	The baseline will be the data collected at Visit 3	Last collection after Visit 3

Abbreviations: ANCOVA = analysis of covariance; CGM = continuous glucose monitoring; CRF = case report form; EAS1 = efficacy analysis set 1; EAS2 = efficacy analysis set 2; MMRM = mixed model repeated measurement; TEAE = treatment-emergent adverse event.

All analyses will be implemented using SAS Enterprise Guide Version 7.1 or above.

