## 4.6. Safety Analyses

Safety measures include treatment exposure, adverse event (AE), vital signs, weight, hypoglycemia, laboratory measures and immunogenicity. All safety analyses will be based on the SS. Unless otherwise specified, safety analysis period will include both treatment period and follow-up period as specified in Section 4.1. Percentages will be calculated using the safety population as the denominator. For events that are gender-specific, the denominator and computation of the percentage will include only participants from the given sex. Unless otherwise noted, Fisher's exact test will be used for treatment comparison, risk difference and 95% confidence intervals will be provided.

For continuous safety variables (for example, laboratory measures, vital signs, and weight), descriptive statistics for the observed values and change from baseline at scheduled visits during the treatment period and follow-up period will be provided. For some selected laboratory measures (i.e. liver enzyme tests, lipid measures), observed values, change from baseline and percentage change from baseline will be analyzed for the log-transformed values by the MMRM model using treatment, visit, and treatment by visit as fixed effects, baseline of the dependent variable as a covariate, and compound symmetry as the variance-covariance structure.

The incidence and event rate of participant-reported and CGM-based hypoglycemia will be summarized by treatment and analysis period for different types of hypoglycemia. Analysis details are provided in Section 0.

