#### 4.6.2.3. Laboratory and Adverse Event for Hepatic Safety

Hepatic labs include

- alanine aminotransferase (ALT)
- aspartate aminotransferase (AST)
- total bilirubin (TBL)
- direct bilirubin (DBL)

- serum alkaline phosphatase (ALP), and
- gamma-glutamyltransferase (GGT).

When criteria are met for hepatic evaluations, investigators will conduct close monitoring of hepatic symptoms and liver tests, perform a comprehensive evaluation for alternative causes of abnormal liver tests, and complete follow-up hepatic safety CRFs.

The table below lists summary TFLs for the analysis of hepatic laboratory data.

Analysis	Details
Abnormal postbaseline categories – hepatic safety parameters	
ALT: The number and percentage of participants with a measurement greater than or equal to 1 time (1X), 3 times (3X), 5 times (5X), 10 times (10X), and 20 times (20X) the performing laboratory ULN during the postbaseline period will be summarized for all participants with a postbaseline value.
 
AST: The number and percentage of participants with a measurement greater than or equal to 1 time (1X), 3 times (3X), 5 times (5X), 10 times (10X), and 20 times (20X) the performing laboratory ULN during the postbaseline period will be summarized for all participants with a postbaseline value.
 
ALP: The number and percentage of participants with a measurement greater than or equal to 2 times (2X) and 3 times (3X) the performing laboratory ULN during the postbaseline period will be summarized for all participants with a postbaseline value.
 
TBL: The number and percentage of participants with a measurement greater than or equal to 2 times (2X), 5 times (5X), and 8 times (8X) the performing laboratory ULN during the postbaseline period will be summarized for all participants with a postbaseline value.
 
DBL: The number and percentage of participants with a measurement greater than or equal to 2 times (2X) and 5 times (5X) the performing laboratory ULN during the postbaseline period will be summarized for all participants with a postbaseline value.
 
GGT: The number and percentage of participants with a measurement greater than or equal to 2 times (2X) the performing laboratory ULN during the postbaseline period will be summarized for all participants with a postbaseline value.

Analysis	Details

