#### 4.6.2.4. Clinical Laboratory Evaluations

For the following selected laboratory measures:

- Liver enzyme tests: ALT, ALP, AST, GGT, DBL and Total Bilirubin
- Lipid measures: Triglycerides, total cholesterol, LDL-C, and HDL-C (results from fasting samples) )

MMRM model (as described in Section 4.6) will be used for the observed values, change from baseline and percentage change from baseline, for which log-transformation will be applied. Geometric LS means will be provided. Analyses will be provided in both international units (SI) and conventional units (CN) if they are different.

Box plots with descriptive statistics for the observed values and change from baseline will be provided by treatment group and visit.

For other laboratory measures, descriptive summaries will be provided for the observed values and change from baseline by treatment group and visit.

The percentages of participants with elevated or low values meeting specified levels (see Appendix 10, Section 6.10) at any time post-baseline (including scheduled and unscheduled measurements) will be summarized and compared between treatment groups using risk difference and 95% confidence interval.

A listing of abnormal laboratory analytes collected quantitatively (high or low during postbaseline period using Level 2 definitions in Appendix 10) and qualitatively (abnormal during postbaseline period) will be provided, including participant identification, treatment group, laboratory sample collection day (that is, days from start of study drug), analyte name, abnormal result, and reference low or high limits (Level 2 cut-off value).

Scatter plots of maximum-by-maximum measurements and minimum-by-minimum measurements will not be created a-priori. They may be created if warranted after review of the planned tables and figures, using Figures 6.3 and 6.4 from the Analysis and Displays for Labs white paper (PHUSE 2022) as the model. ADaM datasets will include variables to enable the creation of scatter plots for use in either an interactive tool or for ad-hoc figures.

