## 6.10. Appendix 10: Abnormality Level Criteria for Chemistry and Hematology Laboratory Results

Parameter	Level 1	Level 2	Level 3
General Chemistry			
Sodium, low (mEq/L)	<132	<130	<125
Sodium, high (mEq/L)	>150	>155	>160
Potassium, low (mEq/L)	<3.6	<3.4	<3.0
Potassium, high (mEq/L)	>5.5	>6	>6.5
Chloride, low (mEq/L)	<95	<88	<80
Chloride, high (mEq/L)	>108	>112	>115
Bicarbonate, low (mEq/L)	<20	<18	<15
Bicarbonate, high (mEq/L)	N/A	N/A	>30
Blood urea nitrogen, high (mg/dL)	>23	>27	>31
Calcium, low (mg/dL)	<8.4	<8.0	<7.5
Calcium, high (mg/dL)	>10.5	>11.0	>12.0
Phosphate, low (mg/dL)	<2.5	<2.0	<1.4
Protein (total), low (g/dL)	<6.0	<5.4	<5.0
Albumin, low (g/dL)	<3.1	<2.5	<2.0
Uric Acid (urate), high (mg/dL)	>7.0	NA	NA
Kidney Function			
Creatinine, increase (mg/dL)	≥1.5 x baseline	≥2.0 x baseline	≥3.0 x baseline
eGFR, decrease (ml/min/1.73m  )	≥25% decrease	≥50% decrease	≥75% decrease
Lipids			
Cholesterol (total), high (mg/dL)	>200	>240	>300
HDL, low (mg/dL), males	<40	<30	<20
HDL, low (mg/dL), females	<50	<40	<20
LDL, high (mg/dL)	>130	>160	>190
Triglycerides, high (mg/dL)	>150	>300	>500
Hematology			
Complete Blood Count			
WBC, low (cells/µL)	<3500	<3000	<1000
WBC, high (cells/µL)	>10,800	>13,000	>15,000
Hemoglobin, decrease (g/dL)	N/A	>1.5 dec. from baseline	>2 dec. from baseline
Hemoglobin, increase (g/dL)	N/A	>2 inc. from baseline	>3 inc. from baseline
Platelets, low (cells/µL)	<140,000	<125,000	<100,000
Hemoglobin, low (g/dL), male	12.5-13.5	<12.5	<10.5
Hemoglobin, low (g/dL), female	11.0 – 12.0	<11	<9.5
WBC Differential			
Lymphocytes, low (cells/µL)	<1000	<750	<500
Lymphocytes, high (cells/µL)	>4000	>10000	>20000
Neutrophils, low (cells/µL)	<2000	<1000	<500

Eosinophils, high (cells/ $\mu$ L)	>650	>1500	>5000
Coagulation Studies			
prothrombin time, increase (sec)	>1.1 x ULN	>1.3 x ULN	>1.5 x ULN

Note: For Liver enzymes, Lilly defined categories will be used.

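### For fixed laboratory cut-offs the SAP counts participants already at the level before the first dose, so the treatment-emergent comparison named in protocol 9.3.5 is not delivered

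*SAP*

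**What the plan says.** Protocol 9.3.5 (closing paragraphs, under the hypoglycemia subheading) gives "treatment-emergent abnormal laboratory measurements" as an example of a categorical safety variable to be compared by Fisher's exact test or logistic regression.

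The operative SAP text is section 4.6.2.4. Participants with values meeting an Appendix 10 level "at any time post-baseline (including scheduled and unscheduled measurements) will be summarized and compared between treatment groups using risk difference and 95% confidence interval". No condition on the baseline value is attached. SAP 4.6 sets the default denominator: "Percentages will be calculated using the safety population as the denominator". The hepatic categories in SAP 4.6.2.3 are built the same way, on counts "during the postbaseline period will be summarized for all participants with a postbaseline value".

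The baseline table in SAP 4.1 has a row for "laboratory values elevated or low, vital signs and body weight categorical measures". It defines a window from screening to the day of first dose, using scheduled and unscheduled values.

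Table 1 of the SAP records the change, "For laboratory analysis, removed shift analysis, treatment emergent high/low and add elevated or low values meeting specified levels", and gives an update of the program-level SAP as the reason. That table is a change log. It shows that the change was deliberate and disclosed, and is not itself the error.

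**The concern.** Most Appendix 10 rows are absolute limits: triglycerides >150, total cholesterol >200, LDL >130, BUN >23, uric acid >7, potassium <3.6. The entry criteria do not limit these analytes, and participants with eGFR down to 30 may enroll. Exclusion criterion 22 admits ALT and AST up to 3x ULN and ALP up to 2.5x ULN, so the ALT/AST >=1X and ALP >=2X categories can also be met before dosing.

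A participant who enters at such a level and stays there is counted as an event. Both arms then carry a similar block of pre-existing cases. These add background to the percentages and contribute nothing to the difference unless treatment changes their course. In a safety table the consequence is that a real rise in new abnormalities is harder to see.

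The SAP uses baseline status elsewhere: maximum baseline severity for TEAEs (4.6.2) and baseline antibody status for treatment-emergent ADA (4.7.1). The fixed-cut-off laboratory rows do not, although 4.1 supplies a window for them. The listing in 4.6.2.4 does not fill the gap, because its stated contents include no baseline value.

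**Working it through.** **Plan's own figure.** The documents give no rate, power or precision target for laboratory abnormalities, so there is none to reproduce. The arm size is consistent: 670/2 = 335 per arm, and 335 x 0.85 = 284.75, against 284 stated completers.

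**Inputs from the documents.** 335 per arm (SAP 5); two-sided 0.05 (protocol 9.3.1).

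**Assumptions, not in the documents.** b = share at the level at baseline (varied); q = share of these who meet it again after baseline, 90% in both arms; new-onset risk among the others, 10% (control) vs 20% (test).

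**Formulas.**
- Any-time rule: P = b x q + (1-b) x p, with n = 335 per arm.
- With equal q, the block b x q cancels, so RD_any = (1-b) x (p_t - p_c).
- Restricted rule: RD = p_t - p_c, with n = 335 x (1-b) per arm.
- Power = Phi(RD/SE - 1.96), where SE = sqrt[p_c(1-p_c)/n + p_t(1-p_t)/n].

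**Worked case, b = 20%.**
- Any-time: control 0.20 x 0.90 + 0.80 x 0.10 = 0.26; test 0.18 + 0.80 x 0.20 = 0.34. RD = 0.08, SE = 0.0353, ratio 2.27, power 62%.
- Restricted: n = 268, RD = 0.10, SE = sqrt[(0.09 + 0.16)/268] = 0.0305, ratio 3.27, power 91%.

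| b | Any-time % (control vs test) | RD, points | Power, any-time | n per arm, restricted | Power, restricted |
|---|---|---|---|---|---|
| 5% | 14.0 vs 23.5 | 9.5 | 89% | 318 | 95% |
| 20% | 26 vs 34 | 8 | 62% | 268 | 91% |
| 50% | 50 vs 55 | 5 | 25% | 167.5 | 74% |

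At b = 50%, 0.45/0.525 = 86% of the counted participants were already at the level at baseline.

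**A smaller effect.** With new-onset risk 5% vs 10% and full persistence, power is 34% (any-time) vs 65% (restricted) at b = 10%, and 12% vs 48% at b = 40%. At b = 0 the two rules coincide (69%).

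**Relaxing equal persistence.** In general, RD_any = b(q_t - q_c) + (1-b)(p_t - p_c). Take b = 50% and the 10% vs 20% risks:
- Persistence 85% vs 95%: 0.475 vs 0.575, RD 10 points, power 74%, the same as the restricted rule.
- Persistence 80% vs 95%: 0.45 vs 0.575, power 90%, better than the restricted rule.

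**Where the rule bites.**
- *Not affected:* creatinine, eGFR decrease and hemoglobin increase or decrease, which Appendix 10 defines relative to baseline; and levels rare at entry, where b is near 0.
- *Categorical contrast affected, but a baseline-adjusted comparison remains:* lipids and liver tests, through the MMRM on log values with baseline as covariate (SAP 4.6, 4.6.2.4).
- *Affected with no other between-arm laboratory comparison:* potassium, BUN, uric acid, WBC and platelets, for which 4.6.2.4 otherwise plans only descriptive summaries.

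**The case against.** The strongest reply is that the any-time contrast is valid under randomization. It compares the proportion abnormal after baseline, and it captures worsening or non-resolution in participants already abnormal, which a restricted rule drops. This stands. The unequal-persistence cases show the any-time rule can match or beat the restricted one, so it should not be replaced or demoted.

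Second, the change is disclosed, the protocol names treatment-emergent laboratory values only as an example, and it leaves details of safety measures to the SAP. This also stands: there is no hidden deviation. However, protocol 9.3.1 and SAP 4.1 call for a justification of changes, and a reference to the program-level SAP does not say why baseline status should be ignored.

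Third, other analyses cover part of the ground. Lipids and liver tests keep the adjusted MMRM. Clinically relevant laboratory changes are reported as AEs, and hypokalemia and hepatic disorders have their own TEAE summaries. A reader might infer that drug effects on laboratory values are diluted throughout; the documents do not support that, since only the fixed-cut-off categorical contrast is attenuated. The AE route, though, depends on investigator reporting and does not replace a laboratory comparison for potassium, BUN, uric acid, WBC or platelets.

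Fourth, the hepatic part is narrow. Criterion 22 makes the higher transaminase, ALP and total bilirubin categories rare at entry, and 4.6.2.3 only says that the counts are summarized, although the general text of 4.6 provides a risk difference and 95% CI by default.

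**Conclusion.** The point holds for the fixed cut-offs in Appendix 10 and for the lower ULN categories in 4.6.2.3 (ALT/AST >=1X, ALP >=2X). The planned count includes participants at the level before the first dose, and the treatment-emergent comparison named in the protocol is missing.

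With equal persistence the risk difference shrinks by exactly (1-b). The loss of power is slight at b = 5% (89% vs 95%) and severe at b = 50% (25% vs 74%). These figures rest on the assumed new-onset risks, on 90% persistence in both arms and on a prevalence b that the documents do not report, so the size in this trial cannot be determined.

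Two stronger readings should be avoided. One is that the SAP 4.1 baseline window goes unused: the baseline-relative rows and the weight-change categories need a baseline, and only the fixed-cut-off rows ignore it. The other is that the any-time percentages cannot be interpreted: they answer a valid but different question. This is an inexpensive gap worth closing in the safety tables and does not touch the trial's efficacy conclusions.

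**What to change.** In SAP 4.6.2.4, and for the lower ULN categories in 4.6.2.3, keep the any-time post-baseline comparison. Beside it, add for each fixed cut-off a treatment-emergent risk difference with 95% CI, among participants who did not meet that level in the SAP 4.1 baseline window and have at least one post-baseline value. State the denominator per analyte and level. Leave the creatinine, eGFR and hemoglobin-change rows as they are.

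The cost is SAP wording, one baseline flag per analyte and level, and one extra set of tables. No new data are needed. Denominators will be smaller for some analytes; the restricted power figures above already allow for that.

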## 1. Introduction

The study protocol contains a summary of the planned statistical analyses of the most important endpoints, including primary and key secondary endpoints. The changes to the analyses described in the protocol and in the prior version of SAP are listed in the Version History section. This SAP includes the analyses details for efficacy, safety measures, patient-reported outcomes, and parameters based on continuous glucose-monitoring (CGM). Pharmacokinetic/pharmacodynamics (PK/PD) analyses will be conducted by the PK/PD group and will be described in the PK analysis plan. The specifications for ADaM data, tables, figures and listings will be described in separate documents.

## 1.1. Objectives, Endpoints, and Estimands

Objectives	Endpoints
Primary	
Demonstrate noninferiority of LY3209590 compared to insulin glargine on glycemic control.	Change in HbA1c from baseline at Week 26
Key Secondary (Multiplicity Adjusted)	
Demonstrate LY3209590 is superior to insulin glargine in the selected parameters of glycemic control.	
 
Change in HbA1c from baseline at Week 26
 
The percentage of participants achieving HbA1c <7% at Week 26 without nocturnal hypoglycemia (<54 mg/dL [3.0 mmol/L] or severe) during treatment phase up to Week 26
 
The event rate of participant-reported clinically significant nocturnal hypoglycemia (<54 mg/dL [3.0 mmol/L] or severe) during treatment phase up to Week 26
 

Other Secondary	
To investigate the effect of LY3209590 compared with insulin glargine in additional parameters of diabetes management.	
 
Change in fasting glucose measured by SMBG from baseline to Week 26
 
Time in glucose range between 70 and 180 mg/dL (3.9 and 10.0 mmol/L), inclusive measured during the CGM session that occurs between Week 22 and Week 26
 
Time in hypoglycemia range with glucose <54 mg/dL (3.0 mmol/L), measured by CGM that occurs between Week 22 and Week 26
 
Time in hyperglycemia range with glucose >180 mg/dL (10.0 mmol/L), measured by CGM that occurs between Week 22 and Week 26
 
Glucose variability measured during the CGM session that occurs between Week 22 and Week 26
 
Insulin dose at Week 26 
 
basal
 
bolus
 
total, and
 
basal/total insulin dose ratio
 
 
 

To investigate the safety of LY3209590 compared with insulin glargine.	
 
Incidence and rate of composite of Level 2 and 3 hypoglycemia events during treatment period
 
Body weight change from baseline to Week 26
 

To investigate the treatment impact of LY3209590 compared with insulin glargine on patient-reported outcome measures.	
 
Treatment experience at Weeks 26 for DID-EQ
 

Tertiary	

 
Investigate the treatment impact of LY3209590 compared with insulin glargine on other measures of efficacy, safety, and patient-reported outcomes.
 
	
Efficacy
 
 
Percentage of participants achieving HbA1c <7% at Week 26
 
Percentage of participants achieving HbA1c <math>\leq 6.5\%</math> at Week 26
 
Change from baseline to Week 26 in fasting serum glucose as measured by central laboratory
 

Objectives	Endpoints
	Safety 
 
Rate and incidence of Level 2 hypoglycemia events during treatment period
 
Rate and incidence of Level 3 hypoglycemia events during treatment period
 
Incidence of positive treatment-emergent antibody of LY3209590
 

	Patient-reported outcomes 
 
Frequency of responses to “Basal Insulin Experience: Likelihood of incorporating into routine” at Week 26
 
Frequency of responses to “Basal Insulin Experience: Preference” at Week 26
 
Change in EQ-5D-5L from baseline at Week 26
 

 
To characterize the PK/PD of LY3209590.
 
	
 
LY3209590 PK and concentration response relationships to key safety and efficacy measures
 

Abbreviations: CGM = continuous glucose monitoring; DID-EQ = Diabetes Injection Device Experience Questionnaire; EQ-5D-5L = EuroQol 5 dimensions 5 levels; HbA1c = hemoglobin A1c; PK = pharmacokinetics; SMBG = self-monitoring of blood glucose.

